2.2 Secondary Objective

- Evaluate patient satisfaction with aromatherapy at completion of study.
- Evaluate the antiemetic administration between **nausea/vomiting symptom** intervention and control groups during the 48-hour intervention time span.
- Evaluate the number and incidence of unit falls pre and post intervention.

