3.2 Secondary Outcome Measures

Patient Satisfaction with Aromatherapy

A brief semi-structured questionnaire will also be administered to evaluate patient satisfaction with the intervention at the 48-hour completion time.

Evaluate the antiemetic administration between **nausea/vomiting symptom intervention and control groups**

Data will also be collected from the electronic medical record related to antiemetic medications administered (dose, route, frequency) during the 48-hour intervention.

Evaluate the number and incidence of unit falls pre and post intervention

Fall rates will also be evaluated using the total number of falls reported to the National Database of Nurse Quality Indicators during the baseline and intervention timeframes. Demographic data will be collected including age, gender, and race/ethnicity.

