The study team initial visit will be at 0 hours (visit 1) and follow-up visits will be completed at 24 hours (visit 2) and 48 hours (visit 3). During visit 2 (Monday-Friday only), the study team will remind participating patients to complete their symptom journal, will answer any study-related questions, and will inquire about any aromatherapy side effects. During visit 3, a study team member will instruct the patient to complete the 48-hour symptom measures in the journal and will complete a brief intervention satisfaction questionnaire (Appendix C) with the patient (intervention group only). Patients will be provided a \$25 gift card to show appreciation for their time in the study. After symptom data collection is completed, a study team member will review and document antiemetic medication administration from the electronic medical record during the 48-hour intervention time frame. **Antiemetic administration will be captured on an Excel spreadsheet on a secure Microsoft Team for intervention and control participants in the nausea/vomiting symptom group. Included medications are scopolamine, lorazepam, promethazine, prochlorperazine, olanzapine, dexamethasone, Marinol, and ondansetron indicated for nausea/vomiting. Medication type, dose, order type (scheduled vs. PRN), and number of doses will be documented for antiemetics administered during the study timeframe.** Concomitant medications (e.g., antiemetic medications, steroids, benzodiazepines) will not be controlled as part of the study as the intent is not to alter standard practice for symptom treatment, but rather to provide an adjuvant to help reduce symptom burden. However, it is reasonable to expect that the need for PRN (available as needed) medications prescribed for nausea/vomiting or anxiety may be less in the treatment group compared to control during the 48 hours of inhaled aromatherapy. Because antiemetic and benzodiazepine medications may contribute to an increase in fall risk (Seppala et al., 2018; Wildes et al., 2018), we also plan to observe fall events during the study timeframe. Unit fall total numbers and incidence data will additionally be obtained from data reported to the National Database for Nurse Quality Indicators (NDNQI) for 12 months prior to implementation and 12 months during study implementation.

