12.0 Statistical Considerations

SAS and/or R statistical packages will be used to analyze primary outcomes, secondary outcomes, and demographic sample data.

Primary Outcomes

Comparisons between the intervention and control groups for differences in the CINVR and anxiety tools will be analyzed using mixed-model ANOVA, with time (baseline, 24 hours, 48 hours) repeated within subject. Chi-square tests will be used to compare the groups for differences in the proportions of patients prescribed medications for nausea/vomiting or anxiety. Separate analyses will be performed for the two symptom groups. A two-sided 5% significance level will be used for all tests.

Sample size justification: With sample sizes of 50 patients within each symptom group, 25 intervention/25 control within each symptom group, the study will have 80% power to detect an effect size of 0.81 between intervention and control within each symptom group, based on a two-sample t-test calculation and a two-sided 5% significance level. The recruitment target will be 112 participants (56 per symptom group) to account for a 10% drop out rate.

Secondary Outcomes

Descriptive statistics will be used to analyze frequencies and percentages of the patient satisfaction questionnaire responses, documented antiemetic administration, and number of unit falls. The number of (1) total antiemetic medication doses and (2) doses for each individual medication (i.e., Ativan, promethazine) will be compared between the control and intervention groups for the nausea/vomiting symptom group. The percentage change for number of falls will be calculated by comparing number of falls 12 months prior to intervention implementation to 12 months during implementation.

Descriptive statistics will be used to summarize the demographics of the study sample (frequencies and percentages for categorical variables, means and standard deviations for continuous variables).

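### Antiemetic use is extracted only for the 48 hours after the first patch; a 24-hour look-back would show whether the arms started level and give a modest, cheap gain in precision

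*Combined protocol and SAP*

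**What the plan says.** Every description of the antiemetic data sets the same window.

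- Section 2.2 states the objective as a comparison between intervention and "control groups during the 48-hour intervention time span".
- Section 3.2 defines the data as "antiemetic medications administered (dose, route, frequency) during the 48-hour intervention".
- Section 7.0 has a team member "review and document antiemetic medication administration from the electronic medical record during the 48-hour intervention time frame", and adds: "Medication type, dose, order type (scheduled vs. PRN), and number of doses will be documented for antiemetics administered during the study timeframe".
- The study calendar (section 8.0) lists antiemetic use only as secondary data gathered after the study visits.

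For analysis, section 12.0 says: "Descriptive statistics will be used to analyze frequencies and percentages of the patient satisfaction questionnaire responses, documented antiemetic administration, and number of unit falls". It then says that total doses and doses of each drug "will be compared between the control and intervention groups for the nausea/vomiting symptom group". It names no test, model or covariate for these counts. A separate sentence under Primary Outcomes reads: "Chi-square tests will be used to compare the groups for differences in the proportions of patients prescribed medications for nausea/vomiting or anxiety". That concerns the proportion prescribed a drug rather than the number of doses, and it too is unadjusted.

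No section plans to extract doses given before the first patch.

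**The concern.** Participants are already inpatients when the first patch goes on, between post-transplant day 4 and day 8 (section 6.0). The chart that supplies the 48-hour doses therefore also holds the doses of the preceding day, which the patch cannot have influenced. The plan uses a pre-intervention value elsewhere: the INVR and the anxiety score have a baseline (section 3.1), and unit falls have a 12-month pre-period (section 7.0).

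Wide differences between patients in antiemetic use are to be expected. Concomitant drugs are left to usual practice, scheduled and PRN orders both count, and entry spans five transplant days and both transplant types. Section 7.0 also states an expectation that PRN need may be lower with aromatherapy, so readers will look to this comparison for an effect. Precision is at stake, as is the reader's ability to judge whether the arms were alike at entry.

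**Working it through.** **Inputs from section 12.0.** 25 per arm in each symptom group, effect size 0.81, 80% power, two-sided 5%, 10% drop-out, 56 recruited per symptom group. **Assumed.** r, the correlation between pre-patch and 48-hour dose counts, is not in the documents; the range used is 0.3 to 0.6.

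**Step 1: the plan's own figure.** Two-sample t-test, noncentrality d × √(n/2) = 0.81 × √12.5 = 2.86 on 48 df: power 0.801, and a detectable d at 80% power of 0.809. Drop-out: 50/(1 − 0.10) = 55.6, so 56 per group and 112 in all. The stated figures reproduce. They were set for the symptom scores; none is given for antiemetic doses.

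**Step 2: effect of a pre-patch covariate.** Residual variance factor = 1 − r². Equivalent patients per arm = 25/(1 − r²). Detectable d and power use the noncentral t with 47 df and the standard error multiplied by √(1 − r²).

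| r (assumed) | Residual variance | Equivalent n per arm | Detectable d, 80% power | Power at d = 0.81 |
|---|---|---|---|---|
| none (as planned) | 100% | 25 | 0.81 | 80% |
| 0.3 | 91% | 27.5 | 0.77 | 84% |
| 0.5 | 75% | 33.3 | 0.70 | 90% |
| 0.6 | 64% | 39.1 | 0.65 | 94% |

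This treats dose counts as roughly normal, and d = 0.81 serves only as a yardstick. Skewed counts would change the figures but not the direction.

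**Step 3: the gain on a count scale.** Two illustrative Poisson-lognormal simulations, each with mean 4 doses per 48 hours, true ratio 0.65, 25 per arm and 4,000 runs per setting. All of these values are assumptions. The second used a 24-hour pre-count with mean 2 and ANCOVA on square-root counts. For the first, the dispersion, pre-window mean and analysis model are not recorded, so its levels cannot be reproduced exactly.

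| Simulation | r | Unadjusted power | Adjusted power | Gain (points) |
|---|---|---|---|---|
| First | 0.31 | 40% | 42% | 2 |
| First | 0.46 | 31% | 37% | 6 |
| First | 0.57 | 24% | 32% | 8 |
| Second | 0.30 | 56% | 57% | 1 |
| Second | 0.46 | 43% | 47% | 4 |
| Second | 0.60 | 33% | 43% | 10 |

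In such a model r rises with the spread between patients, which is why unadjusted power falls down each block. The two differ in level but agree in pattern: next to nothing at r near 0.3, and 4 to 10 points at r of about 0.45 to 0.6.

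**Step 4: chance imbalance.** The difference between two arm means of 25 has standard deviation √(2/25) = 0.283 SD. A gap of at least 0.4 SD in prior use lies 0.4/0.283 = 1.41 standard errors out, a two-sided probability of about 16%. As planned, such a gap in antiemetic use would not be visible.

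**The case against.** The strongest reply is that this is a matter of efficiency and that nothing in the plan is wrong. That stands. A reader might infer that the comparison is biased, or that a chance imbalance could pass for an effect of the oil more often than the nominal 5%. The documents do not support either reading. Allocation is random within symptom group (sections 5.0 to 7.0), so chance differences in prior use are ordinary sampling error, which a valid test or interval already allows for. A simulation with no true effect and 25 per arm gave an unadjusted type I error of 4.3% to 4.8%.

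Four further points can be made.

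- The outcome is secondary and largely descriptive, and the sample size was not set for it. This stands and limits the weight of the point.
- In every simulated setting above, adjusted power stays below 60%. This stands too: the covariate sharpens the estimate but does not make the comparison well powered under those assumptions.
- Other baseline information exists: INVR, chemotherapy regimen and transplant type are collected. A reader should therefore not conclude that nothing is available to adjust for; what is missing is prior antiemetic use. No adjustment is planned for the other variables, and none measures drug use directly.
- Prior use may predict poorly, because symptoms may be changing over days 4 to 8. Scheduled doses could also raise r while being unlikely to respond to the patch. This is fair, and it is why PRN doses need their own comparison.

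The omission is also recoverable, since doses are read from the record after the visits. That makes the change cheap, and it removes urgency apart from the need to pre-specify the covariate before outcome data are seen.

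**Conclusion.** The point holds as a low-cost improvement to a secondary outcome. Sections 2.2, 3.2 and 7.0 confine antiemetic data to the 48 hours after the first patch, section 12.0 compares dose counts without a covariate, and no other section supplies a pre-patch value. The planned comparison remains unbiased, and the stated 80% power is correct for its purpose.

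The loss is precision and a view of how the arms started. If r is 0.3 to 0.6, residual variance is 9% to 36% higher than it need be, as a share of the unadjusted value. The power gain forgone is about 2 to 8 points in the first simulation and 1 to 10 in the second. All of this rests on assumed values for r, the dose mean, the dispersion and the effect. Reporting pre-patch use by arm is worthwhile whatever r proves to be, including if the analysis stays descriptive.

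**What to change.** - **Section 7.0:** extract the same fields (type, dose, scheduled or PRN, number of doses) for the 24 hours before the first patch, as well as for the 48 hours after it.
- **Section 12.0:** pre-specify a between-arm comparison of per-patient 48-hour doses, in total and for PRN doses separately, each with the matching pre-patch count as covariate. Use a negative binomial model, or ANCOVA on square-root counts. Report the estimate with a 95% CI, and tabulate pre-patch use by arm.
- **Sections 2.2, 3.2 and 8.0:** mention the pre-patch window so that all sections agree.

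The cost is one additional 24-hour look-back, on the same spreadsheet and in a chart the team already opens, for about 56 nausea/vomiting participants. It needs no extra visit, patient or procedure. The drawback is that the work buys little precision if r is near or below 0.3.

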8.0 Study Calendar

	Screening	Visit 1	Visit 2 *M-F only	Visit 3	Secondary Data
	Day- Admission	Day 4-8 (0-hours)	Day 5-9 (24-hours)	Day 6-10 (48-hours)	Post Study
STUDY PROCEDURES					
Screen new admissions for inclusion/exclusion criteria	x				
Consent		x			
Demographic Questionnaire		x			
Symptom Assessment Tools		x	x	x	
Apply Patch		x			
Satisfaction Questionnaire- Intervention Group				x	
Remove Patch				x	
Evaluate Antiemetic Use					x
Evaluate Falls					x

9.0 Reportable Events

Inhaled essential oils including lavender, peppermint, and mandarin are generally considered safe if used as indicated. The essential oils used in this study are infused within an adhesive patch, so will not come in direct contact with the skin. However, if the essential oil patch is used not as indicated (e.g. oil applied directly to the skin, oil ingested), the risk of adverse event occurrence may increase.

Adverse Event: Defined as any problematic medical occurrence in a study participant who has received the intervention including inhaled lavender, peppermint, or mandarin essential oil, regardless of possibility of a causal relationship. Adverse events will be documented after the participant begins receiving the intervention.

The occurrence and nature of each participant's medical condition will be documented by study personnel prior to enrollment. Study personnel will document any changes in medical condition and/or the occurrence and description of any adverse event during the study. Events that occur from inhaled essential oil administration up to 72 hours after will be recorded (allows for 24 hours of monitoring after intervention ends). Events will be reviewed during data safety monitoring to determine causality.

Significant Adverse Event: Defined as a life-threatening condition (i.e. immediate risk of dying); severe/permanent disability; a significant hazard, contraindication, side effect, or precaution as deemed by the Data Safety Monitoring team to be caused by the intervention. Investigators will determine causality based on the participant's clinical course, medical history, and administered medications.

Adverse and Significant Adverse Events will be reported to the IRB within 5 business days from discovery if they are determined to be (1) unexpected; (2) related or possibly related to participation in the study; (3) finding suggests that the research procedures involve a greater harm risk than previously anticipated; (4) occurrence of unanticipated adverse device effects.

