4.2 Exclusion Criteria

- Under 18 years of age
- Currently receiving another form of essential oils (e.g., diffuser, essential oil roller, lotion with essential oils) within 24 hours of enrollment
- Intubation
- Medical sedation
- Receipt of chimeric antigen receptor T (CAR-T) cells
- History of atrial fibrillation
- History of seizures/epilepsy
- Adhesive allergy or sensitivity
- Currently pregnant
- Prisoner
- Inability to smell

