5.0 Study Design

This study will be a randomized controlled trial. Prior to randomization, participants will be asked which symptom, nausea/vomiting or anxiety, is most burdensome for them. Participants will be stratified based on their identified symptom of burden (nausea/vomiting or anxiety) and will then be randomized to either the intervention or control group, with a target of 50 participants in the nausea/vomiting symptom group (25 intervention and 25 control) and 50 participants in the anxiety symptom group (25 intervention and 25 control). Intervention and control groups will receive Wyndmere Naturals, Inc. aromatherapy patches and a symptom journal. Participants in the intervention group indicating that nausea/vomiting is the primary symptom of concern will receive peppermint inhaled aromatherapy patches (or mandarin if peppermint intolerance indicated). Participants in the intervention group indicating that anxiety is the primary symptoms of concern will receive lavender inhaled aromatherapy patches. The control group will receive non-scented aromatherapy patches (i.e., blank hydrogel adhesive patches without essential oil infusion), so it will not be feasible to blind participants to group assignment. The control group will have the same interactions with the study team as the intervention group and will complete patch changes and a symptom journal to serve as an attention control.

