After consenting to study participation, patients will complete a brief demographic questionnaire (see Appendix A). Additional patient data (cancer type, chemotherapy regimen, transplant type, unit of hospitalization) will be collected from the electronic medical record by a study team member. Patients will be asked what symptom they find most concerning (nausea/vomiting or anxiety) and will then be randomly assigned to the intervention or control group using a random number table based on symptom of concern. After random assignment, the patient will be educated on how to use a symptom journal (Appendix B) by a study team member and will be asked to complete the baseline symptom measures in the journal. Patients will be instructed to complete the same symptom measures on the following day independently (24 hour follow up). Patients assigned to the intervention group will receive 48 hours (6 patches) worth of essential oil infused (lavender, peppermint, or mandarin) patches. Aromatherapy patches will be applied to the patient's skin containing peppermint, mandarin, or lavender essential oils. Patient indicating that nausea/vomiting is their symptom of concern will receive peppermint as the default oil or mandarin oil if they have a known intolerance to peppermint. Patients indicating that anxiety is their symptom of concern will receive lavender oil. Patients assigned to the control group will receive 48 hours (6 patches) worth of non-scented patches (i.e., blank hydrogel adhesive patches without essential oil infusion). Patients in both groups will be instructed to change the aromatherapy patch (essential oil infused [intervention group] or non-scented [control group]) every 8 hours, as recommended by manufacturer, and document the

patch change in the symptom journal. Patients in both groups will also be instructed to remove the aromatherapy patch and contact the study team with and signs/symptoms of sensitivity to the patch adhesive or essential oil. The study team will post an “aromatherapy in use” sign inside the patient room to notify clinicians that the patient is on study, with instructions to remove the aromatherapy patch before a MRI test.

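### Section 9 ties its 72-hour event window, and on the natural reading its adverse event definition, to essential-oil recipients; neither is stated for blank-patch controls

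*Combined protocol and SAP*

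**What the plan says.** Section 9.0 (Reportable Events) contains four statements that matter here.

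- **Definition of an adverse event:** "Defined as any problematic medical occurrence in a study participant who has received the intervention including inhaled lavender, peppermint, or mandarin essential oil". Events count whatever their cause.
- **Start of documentation:** "Adverse events will be documented after the participant begins receiving the intervention".
- **Window:** "Events that occur from inhaled essential oil administration up to 72 hours after will be recorded". A parenthesis explains that this leaves 24 hours of monitoring once the intervention is over.
- **General duty:** "Study personnel will document any changes in medical condition and/or the occurrence and description of any adverse event during the study".

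Section 9.0 mentions neither the control group nor the blank patch.

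Section 5.0 describes the control product as "blank hydrogel adhesive patches without essential oil infusion". Section 7.0 sets the control schedule: "Patients assigned to the control group will receive 48 hours (6 patches) worth of non-scented patches". Section 7.0 also tells both groups to take the patch off and contact the team if they notice "signs/symptoms of sensitivity to the patch adhesive or essential oil". Section 4.2 excludes patients with "Adhesive allergy or sensitivity".

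**The concern.** Followed as written, Section 9.0 records and classifies events differently in the two arms. The window starts at an exposure that controls never have. The definition names only the three oils.

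Two things are at stake. First, both arms wear the same kind of adhesive, and the protocol itself foresees adhesive reactions. The blank-patch arm is the natural reference for telling a reaction to the adhesive from a reaction to the oil, but a fair comparison needs the same definition and the same period of observation in both arms. Second, the Background section describes transplant patients as prone to treatment complications, and the definition ignores causality. Many recorded events will therefore be background events of transplant, and the oil arm's count is hard to interpret without a matching control count.

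The definition also feeds later steps. Reporting to the IRB applies to adverse and significant adverse events that meet listed criteria, among them relatedness to study participation and unexpected device effects. A control's skin reaction to a blank patch could meet those criteria and yet, on the natural reading, not be an adverse event at all.

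**Working it through.** **1. Reproduce the stated window.** Section 7.0 gives 6 patches, changed every 8 hours; Section 9.0 adds 24 hours.

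- Patch wear: 6 × 8 h = 48 h
- Window: 48 h + 24 h = 72 h, which matches Section 9.0.

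The sum works only if the clock starts at the first patch. Controls also have a first patch, so the same 72 hours can be applied to them without changing the figure.

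**2. Read each Section 9.0 rule against the control arm.**

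| Rule | Anchor in the text | Does it reach controls? |
|---|---|---|
| 72-hour window | Administration of inhaled essential oil | No. Controls receive no oil. |
| Adverse event definition | Receipt of the intervention, with three oils named | Not on the natural reading. A looser reading is possible if the list of oils is only illustrative. |
| Start of documentation | Beginning of the intervention | Ambiguous. Sections 2.2, 3.1, 6.0 and part of 7.0 use the word for both arms; Section 5.0 and other parts of 7.0 set it against control. |

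**3. Check whether other provisions close the gap.**

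| Provision | Reaches controls? | What it lacks |
|---|---|---|
| Section 9.0, changes in medical condition | Yes, no arm limit | No 72-hour window; its mention of adverse events refers back to the disputed definition |
| Section 7.0, sensitivity self-report | Yes, both groups | Covers adhesive or oil sensitivity only |
| Section 7.0, visit 2 question | Yes, participating patients | Monday to Friday only; aromatherapy side effects only |
| Section 10.0, capture of serious adverse events in OnCore | Yes, all such events | Nothing for non-serious events; no 72-hour window |

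None of the four states the definition and window for controls. The study calendar (Section 8.0) shows no participant visit after 48 hours. Between 48 and 72 hours the window sentence is therefore the only text that expressly requires non-serious events to be recorded, and it is tied to oil.

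**4. Size.** Inputs are 25 controls per symptom group at target (Section 5.0) and 56 recruited per symptom group (Section 12.0), taken as split equally.

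- Controls: 2 × 25 = 50 of 100 at target; 2 × 28 = 56 of 112 recruited
- Blank patches: 6 × 50 = 300 to 6 × 56 = 336
- Planned adhesive wear: 48 h × 50 = 2,400 h to 48 h × 56 = 2,688 h
- Time after the last patch: 24 h × 50 = 1,200 h to 24 h × 56 = 1,344 h

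These figures describe exposure and observation time, not harm. They assume that all six patches are worn for 8 hours as instructed.

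**The case against.** The best defence is that this is loose drafting rather than a rule. The protocol calls the patches in both groups aromatherapy patches. Section 7.0 compares treatment with control over 48 hours of inhaled aromatherapy, so a period named after the oil exposure is there applied to both arms. The window's own explanation refers to the end of the intervention, a word often used for both arms. The list of oils in the definition need not be exhaustive. The severe-outcome parts of the significant adverse event definition carry no oil restriction on their face, and the IRB criteria are framed by study participation and device.

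The defence adds that the main rationale is largely served already: both groups have the same instruction to report sensitivity, changes in medical condition are documented in everyone, and all serious events are captured. It also notes that the patch-hour figures only multiply the schedule, and that no safety analysis is planned for either arm.

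Part of this stands. A two-arm reading of the definition is possible, and control events would not go unrecorded. What is most exposed is non-serious events in the 24 hours after the last patch, together with how control events are classified throughout. The exposure figures do not measure harm.

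The rest does not remove the point. The window sentence refers to essential oil administration, which no reading extends to a patch without oil. None of the other provisions supplies the definition and window for non-serious events in controls. If two defensible readings of a safety definition exist, staff may apply different ones.

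**Conclusion.** The point holds. The window gap is explicit; the gap in the definition rests on the natural reading; the documentation start is ambiguous. About half the trial is affected: 50 of 100 participants at target, or 56 of 112 recruited if allocation is equal. The number of events affected cannot be estimated, because the documents give no event rate.

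The weakness is one of definition and timing, not an absence of safety data in controls. Its consequence is modest. Safety is not among the objectives or outcomes (Sections 2.0 and 3.0), Section 12.0 plans no comparison of events by arm, causality is judged case by case (Sections 9.0 and 10.0), and Section 10.0 classes the trial as low risk. The primary efficacy conclusions are unaffected. The change should be made because it is cheap and makes the control arm usable as a safety reference.

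**What to change.** In Section 9.0:

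- Define an adverse event as any problematic medical occurrence in any participant who has received a study patch, whether oil-infused or blank.
- Start documentation, and the 72-hour window already stated, at first patch application in both arms.
- Say how hours 48 to 72 are covered, using the same method in both arms, since the calendar shows no visit then for either.

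In Section 12.0, add a descriptive listing of events by arm, without a test. This is a useful addition, but the Section 9.0 change does not depend on it.

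The cost is wording, one listing, and event entry under the common rule for about 50 to 56 controls. The entry work is real: because the definition ignores causality, many entries will relate to transplant. The listing will be imprecise at this sample size. Controls need no visit or assessment beyond what the oil arm's 72-hour window already calls for.

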All trials conducted at the IUSCC are subject to auditing and/or monitoring per the Institutional DSMP. Reports will be reviewed by the full DSMC at the time of study review.

Data Management/ Oncore Reporting Requirements

The DSMC reviews data and study progress directly from Oncore; therefore, timely data entry and status updates are vital. Study data must be entered within Oncore promptly, no later than one week from study visit occurrence. Subject status in Oncore will be updated in real time, as this may affect overall trial enrollment status. Global SAEs and deviations will be reviewed on a monthly basis by the DSMC Chair directly from Oncore.

Study Accrual Oversight

Accrual data will be entered into the IU Simon Cancer Center OnCore system. The Protocol Progress Committee (PPC) reviews study accrual twice per year, while the PPC coordinator reviews accrual quarterly.

Oncore Safety Reporting

In addition to protocol- and regulatory-required safety reporting, all serious adverse events (SAEs) will be captured in the Oncore system within 1 business day of notification. Initial SAE reporting will include as much detail as available, with follow-up to provide complete

information. Attributions will be assessed to study drugs, procedures, study disease, and other alternate etiology.

Protocol Deviation Reporting

Protocol deviations will be entered into OnCore within 5 days of discovery and reviewed by the DSMC Chair on a monthly basis. Findings will be reported to the full DSMC at the time of study review. For serious or repetitive protocol deviations, additional action may be required by the DSMC.

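### The adverse-event definition and its 72-hour window are worded around essential oil, so blank-patch controls have no explicit matching rule for non-serious events

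*Combined protocol and SAP*

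**What the plan says.** Section 9.0 (Reportable Events) contains three statements that matter here.

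- The definition: "Defined as any problematic medical occurrence in a study participant who has received the intervention including inhaled lavender, peppermint, or mandarin essential oil". It applies whatever the cause, and documentation begins once the participant starts receiving the intervention.
- The window: "Events that occur from inhaled essential oil administration up to 72 hours after will be recorded". The protocol explains the length as leaving a further day of monitoring after the intervention ends.
- A general duty: "Study personnel will document any changes in medical condition and/or the occurrence and description of any adverse event during the study". It is not limited by arm and states no number of hours.

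Section 5.0 (Study Design) describes the comparator: "The control group will receive non-scented aromatherapy patches (i.e., blank hydrogel adhesive patches without essential oil infusion"). The same section says controls are to have the same contact with the study team, as an attention control.

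Other safety capture also reaches controls:

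- Section 7.0 (Study Procedures): "Patients in both groups will also be instructed to remove the aromatherapy patch and contact the study team with and signs/symptoms of sensitivity" to adhesive or oil.
- Section 7.0, visit 2 (weekdays only): the team "will inquire about any aromatherapy side effects". This is addressed to participating patients in general.
- Section 10.0 (Data Safety Monitoring): "all serious adverse events (SAEs) will be captured in the Oncore system within 1 business day of notification". There is no restriction by arm.

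Section 12.0 (Statistical Considerations) plans no safety comparison, and safety is not among the objectives or outcomes in sections 2.0 and 3.0.

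**The concern.** In a randomised comparison, events should be defined and timed in the same way in both arms. Here the definition names the oils, and the clock starts with an exposure that controls never have. A study nurse following section 9.0 to the letter would log a non-serious event on day 3 for a scented-patch participant. For a control with the same event, the nurse would find no equivalent instruction.

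What is at stake is limited but real. The patches are worn between post-transplant days 4 and 10, when background illness is to be expected, and the definition counts events of any cause. The protocol itself anticipates reactions to either adhesive or oil. The blank-patch arm is the natural reference for telling adhesive from oil, and background from treatment. That reference is weaker if non-serious events in controls are not recorded on the same terms.

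**Working it through.** This is mainly a question of wording, so the statements are set side by side. The only figure in the rule is reproduced first.

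**The window.** Section 7.0 gives 6 patches, changed every 8 hours: 6 × 8 h = 48 h. Section 9.0 adds 24 h: 48 + 24 = 72 h. The stated 72 hours reproduces. Controls also receive 6 patches over 48 hours, so the same arithmetic would give them 72 hours if their clock had a start.

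**Does each rule reach a control participant?**

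| Rule | Reaches controls? | Same all-cause definition and same 72 h? |
|---|---|---|
| Adverse-event definition (9.0) | Unclear: depends on how intervention is read | Not explicitly |
| 72-hour window (9.0) | No: starts at oil inhalation | No |
| Changes in medical condition (9.0) | Yes | Any cause, but no hours stated |
| Sensitivity self-report (7.0) | Yes | Sensitivity only |
| Visit 2 inquiry (7.0) | Yes | Side effects only, at one visit |
| Serious events to OnCore (10.0) | Yes | Serious events only |

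**How far the word intervention stretches.** Section 7.0 reviews antiemetic use "during the 48-hour intervention time frame", and that review covers intervention and control participants. So the word is sometimes used for a period common to both arms, and the definition could be read to include blank patches. Against this, section 7.0 labels scented patches as the intervention group and unscented patches as the control group when it describes patch changes. The window sentence names essential oil outright, so a generous reading of intervention does not repair it.

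**Reach.** Section 12.0 gives 25 controls in each of two symptom groups: 25 + 25 = 50 of 100 at target. The recruitment target is 112, so with 1:1 allocation 112 / 2 = 56 controls.

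**Size of bias.** It would depend on the non-serious event rate and on the share of control events that would still be recorded under the general duty. The documents give neither, so no figure can be put on it.

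**The case against.** The strongest reply is that ascertainment is already matched in practice. Section 9.0 documents each participant's medical condition before enrolment and changes to it during the study, without regard to arm, seriousness or cause. Controls get the same study-team contacts. The visit 2 question goes to everyone, visit 3 at 48 hours also applies to both arms, and where an item is for one arm only (the satisfaction questionnaire) the protocol says so. Causality is judged from clinical course, history and medication, with the medical team consulted if needed, and that method does not use a control rate. The trial is monitored as low risk, and no safety comparison is planned.

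Most of this stands, and it rules out several stronger readings.

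- A reader might infer that controls have no safety monitoring. The documents show otherwise.
- A reader might count the weekday-only visit 2, or the single time point it covers, as evidence of a difference between arms. It is not: the schedule is the same in both arms, and visit 3 follows at 48 hours.
- A reader might call the direction of bias certain. It is only probable. It depends on section 9.0 being followed literally, and on someone producing a by-arm table that is not planned.

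One might also say that section 10.0 gives no window for serious events either, so a missing window is weak evidence of harm. But that rule treats both arms alike. The difficulty in section 9.0 is that a stated definition and window apply to one arm and not explicitly to the other. The general duty to note changes in condition does not supply the missing label or time limit.

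**Conclusion.** The point holds as a mismatch of wording. For non-serious events, section 9.0 gives the oil arm an explicit definition and a 72-hour window, and gives blank-patch controls no explicit counterpart. Controls are half the trial (50 of 100 at target; 56 of 112 recruited, assuming 1:1 allocation).

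The likely consequence is more complete recording in the oil arm, which would make any by-arm count of non-serious events unreliable and probably tilted against the oils. This assumes that staff apply section 9.0 literally and that the general documentation duty does not fully compensate. The magnitude cannot be estimated from the documents.

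A reader might infer that a planned result is compromised. The documents do not support that: no efficacy analysis uses these records, section 12.0 contains no safety comparison, and serious-event capture is not restricted by arm. Severity is low; this is an optional, cheap improvement.

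**What to change.** In section 9.0:

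1. Define an adverse event as any problematic medical occurrence, regardless of cause, in any participant who has applied a study patch (scented or blank).
2. Start the window at first application of a study patch (scented or blank), and keep the 72 hours.
3. State that the same recording procedure is used in both arms.

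Optionally, add one descriptive line to section 12.0: number and percentage of participants with at least one event, by arm, with no test.

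The cost is a short amendment and modest extra recording for about 50 to 56 controls, most of it background illness. No new participants or visits are needed, and sample size and power do not change. The optional count would be imprecise. With zero events the exact (Clopper-Pearson) 95% upper limit is 1 − 0.025^(1/n), which gives 7.1% for n = 50 and 6.4% for n = 56. Participants know their assignment, so self-report could still differ between arms after the change.
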